12.4 Missing Values and Model Violations

The possibility of bias from missing data of subjects who prematurely discontinue for reasons possibly related to study drug will be addressed. If it is concluded that there may be a bias of meaningful magnitude as a result of premature discontinuation, a value may be imputed for the missing pharmacokinetic parameter or missing concentrations. Sensitivity analyses might be carried out with the missing value replaced over a range of values.

In some cases of a missing individual concentration value, values of pharmacokinetic variables (C_{\max} , AUC, etc.) will be determined without replacing missing individual concentration values, but simply using the available data. However, if a missing individual concentration value results in a value of a pharmacokinetic parameter that may be too low or too high to a meaningful degree, the value of the pharmacokinetic parameter will tentatively be considered missing. In this case, a value for the missing individual concentration may be imputed so that an appropriate value of the pharmacokinetic parameter can be included in the analysis. The imputed value will be obtained using appropriate methodology that takes into account the individual characteristics of the subject. Also, if the concentration value at the beginning or end of the dose interval is missing, a value must be imputed in order for a value of AUC to be determined.

An imputed value will be obtained using appropriate methodology that takes into account the individual characteristics of the subject. The dataset from which the value is imputed will be restricted to that of subjects whose data could be considered a random sample from the probability distribution applicable to the subject with the missing data. Ordinarily, the dataset from which the imputed value is obtained would be that of the treatment group to which the subject with the missing value is a member, or some appropriate subset of the treatment group, using only subjects who do not have missing values of their own that would make them unsuitable for the purpose.

Transformation of variables in order to avoid a meaningful degree of non-normality in the probability distributions is discussed in Section 12.3. The primary purpose of a transformation will be to have a random variable with an approximately symmetric probability distribution, but an approximately symmetric distribution with apparently very heavy tails (e.g., kurtosis coefficient, as defined in the SAS Procedure Univariate, exceeding 9) would also be of concern. If an adequate transformation is not found for a variable, then a non-parametric analysis may be performed.

13.0 Analysis of Biomarker Research Variables

Descriptive statistics will be provided for each variable by treatment and scheduled time of measurement. The statistics will consist of: number of observations (n), mean, standard deviation, coefficient of variation as a percentage (quotient of standard deviation and mean, multiplied by 100), minimum, median and maximum. If the logarithmic transformation is employed for the analysis of a variable, the geometric mean will also be reported.

An ANCOVA model will be used to evaluate CSF concentrations for total tau, free tau and the ratio of free tau concentration to total tau concentration for each scheduled time of evaluation during treatment. A corresponding analysis will be performed on plasma total tau concentration and on other plasma tau variables for which data are reported. The observations will be classified by treatment and geographical region (as identified in Section 10.7). The initial model will have a term for the interaction of treatment and region. The baseline value for total tau and free tau (last value before the first dose of study drug) will be the covariate in the case of total tau and free tau, but for the analysis on the ratio the covariate will be the baseline total tau concentration measurement. The term for the interaction of treatment and region will be removed if the statistic for this term is not significant at level 0.050. Within the framework of the analysis of covariance model, the hypothesis of no difference between main effects of the higher ABBV-8E12 dose and placebo will be tested at significance level 0.05. If this hypothesis is rejected, the hypothesis of no difference between the lower ABBV-8E12 dose and placebo will then be tested at significance level 0.050. The SAS least squares means corresponding to the treatment main effects (a composite estimate for the three regions) will be provided. If the term for the interaction of treatment and region is retained in the final model, the testing procedure described for the main treatment effects will be carried out for each region, and the SAS least squares means will be provided for all the combinations of region and treatment.

For the analysis of a tau concentration variable, the conditions on the time that a sample is obtained in order for a measurement to be included in an analysis for a planned time are

given in the table below. If a measurement qualifies for more than one of the times, it will be used only for the time that is nearest the actual time of the sample (in terms of Rx Day).

Scheduled Time	Conditions on Time of Blood or CSF Sample
Week 12 (Cohort 1 and Cohort J1 only)	Rx Day 71 – 99, after at least four doses, between 21 and 35 days after the last previous dose
Week 14 (Cohort 1 and Cohort J1 only)	Rx Day 85 – 113, after at least four doses, between 7 and 21 days after the last previous dose
Week 24	Rx Day 141 – 197, after at least six doses, between 21 and 35 days after the last previous dose
Week 28	Rx Day 169 – 225, after at least seven doses, between 21 and 35 days after the last previous dose
Week 48	Rx Day 281 or later, after at least 10 doses, 21 to 35 days after the last previous dose administered
Week 52	Rx Day 281 or later, after at least 11 doses, 21 to 35 days after the last previous dose administered

If the probability distribution for a variable appears to have considerable non-symmetry (e.g., skewness coefficient > 1.00 in magnitude), a transformation will be sought that has an approximately normal distribution. If a transformation is employed, estimates of central values on the original scale (back transformation of SAS least squares means) will be provided in place of the SAS least squares means referred to above. If the logarithmic transformation is used, the comparison of the treatments will be in terms of the ratio of central values.

If data are reported for CSF NFL concentration, serum or plasma NFL concentration, other continuous variables, or count variables that can be appropriately analyzed as a continuous variable (perhaps after transformation), then descriptive statistics will be provided and an analysis like that described for the tau concentration variables will be performed. If data for other types of variables are reported, appropriate descriptive statistics and analyses will be provided.

The association between the variables referred to here as biomarkers and measures of clinical efficacy will be explored.

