8.1.5 Biomarker Analyses

An ANCOVA model will be used to evaluate CSF concentrations for total tau, free tau, and NFL for each scheduled time of evaluation during treatment. Corresponding analyses on plasma measurements of total tau and NFL will be performed. The observations will be classified by treatment and region, and the initial model will have an effect for the interaction of treatment and region. The baseline value for total tau and free tau (last value before the first dose of study drug) will be the covariate in the case of total tau and free tau, but for the analysis on the ratio the covariate will be the baseline total tau concentration measurement. If the test statistic on the interaction of treatment and region is not significant at level 0.050, the effect for interaction will be removed from the model. Within the framework of the analysis of covariance the means of the three treatments (with adjustment for baseline) will be estimated. The hypothesis of no difference between the main effects of the higher ABBV-8E12 dose and placebo will be tested at significance level 0.05. If this hypothesis is rejected, the hypothesis of no difference between the lower ABBV-8E12 dose and placebo will then be tested at significance level 0.050. If the statistic on the interaction of treatment and region is significant at level 0.050, the tests for the comparison of the ABBV-8E12 dose levels to placebo will also be performed for each region within the framework of the final model.

If the probability distribution for a variable appears to have considerable non-symmetry (e.g., skewness coefficient > 1.00 in magnitude), a transformation will be sought that has an approximately normal distribution. If a transformation is employed, estimates of central values on the original scale (back transformation of SAS least squares means) will be provided. If the logarithmic transformation is used, the comparison of the treatments will be in terms of the ratio of central values.

If data for other variables are reported, descriptive statistics will be provided and appropriate analyses performed. The association between the variables referred to here as biomarkers and measures of clinical efficacy will be explored.

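### The Week 52 plasma tau and NFL contrasts ignore the Week 28 values of subjects who have left, and some discontinuation samples have no analysis time

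*SAP*

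**What the plan says.** SAP section 13.0 evaluates CSF total tau, free tau and their ratio by ANCOVA "for each scheduled time of evaluation during treatment". The model has treatment, region and, at first, their interaction. The baseline value "will be the covariate in the case of total tau and free tau". For blood the SAP adds: "A corresponding analysis will be performed on plasma total tau concentration and on other plasma tau variables for which data are reported". For NFL, if data are reported, "an analysis like that described for the tau concentration variables will be performed". Protocol section 8.1.5 agrees: "Corresponding analyses on plasma measurements of total tau and NFL will be performed".

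A table in SAP 13.0, introduced as applying to a tau concentration variable, decides which sample counts for which time:

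- The Week 28 row takes samples from Days 169 to 225 once seven doses have been given, provided the latest dose was 21 to 35 days before.
- The Week 48 row opens at Day 281 and requires 10 or more doses, with that same interval since dosing.
- For Week 52 the condition reads: "Rx Day 281 or later, after at least 11 doses, 21 to 35 days after the last previous dose administered".

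A sample that meets more than one row is used only for the nearest time by Rx Day.

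Protocol Appendix C and SAP Table 2 schedule blood biomarkers at screening, Week 12 (Cohorts 1 and J1 only), Week 28, and Week 52 or premature discontinuation. None is scheduled at Week 48. Section 13.0 has no repeated-measures model, imputation or missing-data sensitivity analysis. The text on discontinuation bias in SAP 12.4 concerns pharmacokinetic variables. An MMRM is planned for the primary scale (SAP 10.2), for the secondary and exploratory longitudinal measures (10.3) and for serum drug concentrations (12.3).

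**The concern.** An ANCOVA fitted at Week 52 alone drops every subject without a qualifying Week 52 sample. It is unbiased if missingness depends only on treatment, region and baseline. An MMRM also allows missingness to depend on the Week 28 value, which has been collected and is informative.

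There is reason to want that protection. Protocol 6.1.8 provides for withdrawal recorded as disease progression, and Protocol 5.3.6.1 measures neurofilament to look at neurodegeneration, so leaving may be related to the marker. If subjects with higher NFL leave and the arms lose different numbers, the Week 52 contrast shifts. It moves toward the null if placebo loses more and away from it if the active arm loses more.

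Two gaps in sample assignment add to this. Some discontinuation samples that the protocol collects have no analysis time. It is also unclear whether the dose-count and 21-to-35-day conditions, which suit a tau-binding marker, carry over to NFL. If they do, the NFL comparison is restricted to subjects who stayed and were dosed.

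**Working it through.** **1. The plan's own use of 25% missing.** SAP 4.3 gives about 90% power for an effect size of 0.56, with 110 per arm, 25% without Week 52 data, and Bonferroni at two-sided 0.025 per dose. Evaluable: 110 × 0.75 = 82.5 per arm. Power = Φ(0.56 × √(82.5/2) − 2.241) = Φ(1.355) = 91.2%, so the figure reproduces. It is stated for the PSPRS; the documents give no missing-data rate for biomarkers. Applying 25% to them is an assumption.

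**2. Subjects with a Week 28 value but no Week 52 value.**

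- Constant hazard: lost by Week 28 = 1 − 0.75^(28/52) = 14.4%. That leaves 94.2 per arm at Week 28, and 94.2 − 82.5 = 11.7 per arm, or 35 in all.
- Linear dropout: 0.25 × 28/52 = 13.5%. That leaves 95.2 per arm, and 12.7 per arm, or 38 in all.
- Bounds: 0 if all leave before Week 28; 3 × 27.5 = 82.5 if all leave after.

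**3. Where a discontinuation sample goes.** Dose days come from the schedule. Week 52 is taken as Day 365 (337 + 28), which is an assumption. Samples are taken 21 to 35 days after the last dose.

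| Last dose (day) | Sample days | Result under the SAP 13.0 table |
|---|---|---|
| 9 (197) | 218–232 | Week 28 to Day 225; no row from Day 226 |
| 10 (225) | 246–260 | no row |
| 11 (253) | 274–288 | no row to Day 280; from Day 281 meets Weeks 48 and 52 |
| 12 (281) | 302–316 | meets Weeks 48 and 52 |
| 13 (309) | 330–344 | meets Weeks 48 and 52 |
| 14 (337) | 358–372 | Week 52 |

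After last doses 11 to 13, every qualifying sample is nearer Day 337 than Day 365. Day 344, for example, is 7 days from the first and 21 from the second. The nearest-time rule, read literally, sends all of them to Week 48. If Week 48 is not a live time for plasma, they stay in Week 52.

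**4. Bias of the Week 52 contrast.** All inputs here are assumed. Large-sample simulation of correlated normal baseline, Week 28 and Week 52 values; 30% versus 20% total dropout; the share 28/52 of dropout falls before Week 28 at random; later dropout is logistic in the Week 28 value (slope 0.5 to 1.5 per SD); true effect 0 or 0.28 SD (the PSPRS low-dose figure, as none is stated for biomarkers), half of it present at Week 28.

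| Analysis | Bias |
|---|---|
| Unadjusted completers (not planned) | 0.02–0.06 SD |
| Planned ANCOVA, all correlations 0.70 or 0.85 | about 0.004–0.011 SD, reaching 0.015 at slope 1.5 |
| Planned ANCOVA, baseline–Week 52 correlation 0.55 | up to about 0.03 SD |
| Planned ANCOVA, baseline–Week 52 correlation 0.30 | up to about 0.05 SD |
| MMRM with Weeks 28 and 52 | within 0.003 SD |

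As a share of 0.28 SD: 0.004/0.28 = 1.4%, 0.011/0.28 = 3.9%, 0.05/0.28 = 18%. With 25% dropout in both arms, the ANCOVA bias is zero within simulation error.

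For scale, the ANCOVA standard error is √(2/82.5) × √(1 − r²), where r is the baseline–Week 52 correlation. It is 0.082 SD at r = 0.85, 0.111 at 0.70 and 0.149 at 0.30. The bias is therefore at most about a seventh of a standard error in the high-correlation cases (0.015/0.111) and about a third in the weakest case (0.05/0.149).

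**5. Precision.** SE ratio, MMRM to ANCOVA = √(1 − p² × (1 − n52/n28)), where p is the Week 28–Week 52 correlation after baseline adjustment. With linear dropout, 1 − 0.75/0.865 = 0.133.

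- All correlations 0.70: p = 0.70/1.70 = 0.412; ratio 0.989; gain 1.1%.
- All correlations 0.85: p = 0.85/1.85 = 0.459; ratio 0.986; gain 1.4%.
- Baseline correlations 0.70 (Week 28) and 0.55 (Week 52), and 0.85 between the two visits: p = 0.465/√(0.51 × 0.6975) = 0.780; ratio 0.959; gain 4.1%.

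**The case against.** The strongest reply is that little is at stake. The baseline covariate already absorbs most of the dependence of dropout on the marker. The remaining bias needs an imbalance in dropout that the documents do not predict. The biomarkers are exploratory, sit outside the family-wise error control, and may not be reported in the study report (SAP 4.8.1). The Week 28 data are also still analysed at Week 28. All of this stands and limits the size of the point. It does not supply an analysis time for Days 226 to 280, settle the NFL rule, or provide a missing-data approach.

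Three stronger readings are tempting but not supported:

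- A reader might infer that anyone who withdraws after Week 28 adds nothing to Week 52. A well-timed sample on or after Day 281, after at least 11 doses, meets the Week 52 row; it is lost to Week 52 only if the nearest-time rule moves it to Week 48.
- A reader might infer that the SAP imposes the dose-count conditions on NFL. The table is written for tau, and NFL is tied to it only by a phrase about a like analysis. The position is unclear rather than fixed.
- A reader might put the bias at 0.02 to 0.06 SD, or 7 to 21% of a 0.28 SD effect. That describes unadjusted completer means, and the SAP adjusts for baseline.

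**Conclusion.** The point holds as a modest improvement to an exploratory analysis. From the text alone, the Week 52 contrast makes no use of Week 28 values, samples on Rx Days 226 to 280 have no analysis time, samples after last doses 11 to 13 can be diverted to a week with no scheduled plasma, and the NFL sample rule is undefined.

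The size rests on assumptions: the PSPRS no-data rate, the dropout pattern, the 30% versus 20% imbalance and the correlations. On these, about 35 to 38 subjects have an unused Week 28 value. ANCOVA bias is about 0.004 to 0.011 SD with baseline correlations of 0.70 to 0.85, and up to about 0.03 to 0.05 SD with weaker baseline–Week 52 correlation. It is about zero under equal dropout. No primary, key secondary or safety conclusion depends on it.

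**What to change.** In SAP 13.0 and Protocol 8.1.5:

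- Analyse plasma or serum total tau and NFL with one MMRM on the (transformed) values at Week 12 (Cohorts 1 and J1), Week 28 and Week 52. Include treatment, region, visit, treatment-by-visit, baseline and baseline-by-visit. Keep the planned treatment-by-region test and its removal rule, and the high-then-low-dose order.
- For NFL, assign all samples, including discontinuation samples, by contiguous Rx Day windows. A midpoint split between Weeks 28 and 52 falls at (197 + 365)/2 = Day 281. State which sample is used when a scheduled and a discontinuation sample share a window; the nearest-day rule in SAP 6.2 would usually keep the scheduled one. Show the dose-conditioned analysis as supportive.
- For tau, keep the dose and timing conditions, and say that samples on Days 226 to 280 are left out on purpose.
- Do not treat Week 48 as an analysis time for plasma.
- Keep ANCOVA for CSF, where Cohort 2 has one post-baseline sample.

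The cost is SAP and protocol wording and some programming, with no new samples or subjects. The downside is that some NFL samples will come from subjects who stopped dosing early, so the plan should say that the NFL contrast includes them.

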14.0 Summary of Changes

There are some changes in the planned analyses from the protocol (original protocol, protocol Amendment 1, Amendment 2, Amendment 3, Amendment 4) to Statistical Analysis Plan version 1.0. The multiplicity adjustment method using Dunnet's test at interim analyses have changed to using Hochberg procedure in Amendment 3 and in the current SAP. Detailed multiplicity adjustment method is added in protocol Amendment 3 and is reflected in Section 10.6 for multiplicity method change in the SAP. The sample size increase from 180 (in protocols prior to Amendment 3) to 330 (Amendment 3) and including Japan in Study M15-562 are reflected in the current SAP. These changes are reflected in Section 4.3. Analysis of the primary efficacy variables and safety variables analysis by geographical region are included in Section 10.7 and Section 11.0 of the current SAP, respectively.

Appendix A. Potentially Clinically Significant (PCS) Laboratory Value

Clinical Laboratory Tests	Very Low (VL)	Very High (VH)
Hematology		
Activated partial thromboplastin time	NA	> ULN
Hemoglobin	< 100 g/L (6.2 mmol/L)	> 40 g/L above ULN
Prothrombin Intl. Normalized Ratio	NA	> ULN
Leukocytes	< $2 \times 10^9/L$	> $100 \times 10^9/L$
Lymphocyte	< $0.5 \times 10^9/L$	> $20 \times 10^9/L$
Neutrophil	< $1 \times 10^9/L$	NA
Platelets	< $75 \times 10^9/L$	NA
Chemistry		
Bilirubin	NA	> $1.5 \times ULN$
Cholesterol	NA	> 12.92 mmol/L (500 mg/dL)
Creatinine	NA	> $1.5 \times ULN$
Calcium (corrected serum)	< 1.75 mmol/L (7.0 mg/dL)	> 3.1 mmol/L (12.5 mg/dL)
Glucose (fasting)	< 2.2 mmol/L (40 mg/dL)	> 13.9 mmol/L (250 mg/dL)
Potassium	< 3.0 mmol/L	> 6.0 mmol/L
Triglycerides	NA	> 5.7 mmol/L (500 mg/dL)
Urate	NA	> 590 umol/L (10 mg/dL)
Albumin	< 20 g/L	NA
Sodium	< 130 mmol/L	> 155 mmol/L
Phosphate	< 0.6 mmol/L (2.0 mg/dL)	NA
Enzymes		
Alanine aminotransferase (ALT)	NA	> $3 \times ULN$
Alkaline phosphatase	NA	> $2.5 \times ULN$
Aspartate aminotransferase (AST)	NA	> $3 \times ULN$

NA = not applicable; ULN = upper limit normal

Note: Adapted from the Common Terminology Criteria for Adverse Events (CTCAE) Version 4.0 Published: May 28, 2009 (v4.03: June 14, 2010).

Appendix B. Criteria for Potentially Clinically Significant Vital Sign and Weight Values

Vital Signs	Very Low (VL)	Very High (VH)
Systolic Blood Pressure (SBP) (mmHG)	≤ 90 and decreased ≥ 30 from baseline	≥ 180 and increased ≥ 40 from baseline
Diastolic Blood Pressure (DBP) (mmHG)	≤ 50 and decreased ≥ 20 from baseline	≥ 105 and increased ≥ 30 from baseline
Pulse (bpm)	≤ 45 and decreased ≥ 30 from baseline	≥ 120 and increased ≥ 30 from baseline
Temperature (C)	≥ 1.1 decrease from baseline	> 38.5 or increase ≥ 1.1 from baseline
Orthostatic SBP (Hypotension) (mmHg)	Decrease of ≥ 30 in SBP (supine to standing)	NA
Orthostatic DBP (Hypotension) (mmHg)	Decrease of ≥ 20 in DBP (supine to standing)	NA
Orthostatic pulse (bpm)	NA	Increase ≥ 30 bpm (supine to standing)
Weight (kg)	Decreased ≥ 7% from baseline	Increased ≥ 7% from baseline

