6.1.7 Toxicity Management

For the purpose of medical management, all adverse events and laboratory abnormalities that occur during the study must be evaluated by the investigator.

A drug-related toxicity is an adverse event or laboratory value outside of the reference range that is judged by the investigator or AbbVie as a "reasonable possibility" of being related to the study drug (Section 6.1.3). Toxicity is deemed "clinically significant" based on the medical judgment of the investigator. The following guidelines should be used for study drug-related toxicity management.

Potential Drug-Related Toxicities

No potential drug related toxicities were identified from preclinical or clinical studies conducted to date. Examples of safety concerns that could be hypothetically associated

with ABBV-8E12 and safety concerns associated with monoclonal antibodies, in general, are summarized below.

On-Target Toxicities

The brain appears to be the only organ to express tau at significant levels. Tau is an intracellular protein mainly expressed in neurons, although lower levels can be found in astrocytes and oligodendrocytes. ABBV-8E12 is directed against extracellular tau and no function of extracellular tau has been reported. No cellular uptake of the mouse version of ABBV-8E12 antibody bound to tau aggregates was detected in preclinical studies.²⁸ The likelihood of adverse on-target side effects of an anti tau immunotherapy is therefore anticipated to be low.

Non-Specific Off-Target Toxicities

Potential toxicities resulting from the non-human origin of ABBV-8E12 include allergic reactions or infusion reactions, including anaphylaxis or anaphylactoid reactions, flu-like symptoms, including fever, fatigue or loss of appetite, or rash. ABBV-8E12 is lacking the Fragment Crystallizable (Fc) effector function activity and therefore Fc-mediated antibody-dependent cellular cytotoxicity and complement-dependent cytotoxicity is not expected. In addition, ABBV-8E12 exhibited a favorable in vitro immune-safety profile. No infusion reactions have occurred in the single dose PSP clinical study or in the Expanded Access protocol (Studies C₂N-8E12-EA-001 and C₂N-8E12-DE-003).

Allergic Reactions Management

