11.4.2 Potentially Clinically Significant Vital Sign and Weight Values

Criteria for potentially clinically significant values have been predefined for selected vital sign and weight variables as outlined in [Appendix B](#). For each variable, a summary of the number and percentage of subjects in each treatment group who have at least one double blind observation that meets the PCS criteria and is more extreme than their baseline value will be provided. A listing will also be prepared that will include, for each variable, all observations for each subject that met the PCS criteria for that variable at any time during the study. PCS analysis for vital sign and weight will also be conducted by geographical region. No comparisons of treatment groups will be performed.

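### The temperature 'Very High' criterion in SAP Appendix B works as a change-only rule for almost every baseline, so its count pools normal readings with fever; report the two parts as separate rows

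*SAP*

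**What the plan says.** Protocol section 8.1.6.3 leaves the PCS definitions for vital signs to the SAP, so SAP Appendix B is where they are set. The relevant text is:

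- **Temperature, Very High** (Appendix B): "> 38.5 or increase ≥ 1.1 from baseline". Either part is enough.
- **Blood pressure and pulse** (Appendix B): these need both parts. Systolic pressure is Very High at "≥ 180 and increased ≥ 40 from baseline"; pulse is Very Low at "≤ 45 and decreased ≥ 30 from baseline".
- **QTcF** (Appendix C): the absolute limit (above 499 msec) and the change limit (increase above 60 msec) stand in two separate rows.
- **Counting** (SAP 11.4.2): a subject enters the summary with "at least one double blind observation that meets the PCS criteria and is more extreme than their baseline value". All qualifying readings are also listed, the analysis is repeated by region, and the arms are not formally compared.
- **Baseline** (SAP 6.2): one value, the last non-missing one before the first dose.
- **Visits** (SAP 6.2): vital signs have 17 post-baseline analysis weeks in Cohort 1 and Cohort J1. Cohort 2 has 14, because Weeks 1, 13 and 14 do not apply to it.

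**The concern.** Long-term safety is one of the two primary objectives. Protocol section 6.1.7 lists flu-like "symptoms, including fever, fatigue or loss of appetite, or rash" among the potential toxicities of the antibody. The PCS summary is where a reader would look for the number of subjects per arm with a measured fever, and with this rule that number cannot be read from it. A rise of 1.1 °C that ends in the normal range and a temperature of 39 °C each add one to the same count. The requirement that the value be more extreme than baseline filters nothing here, because any rise of 1.1 meets it.

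If ordinary variation between visits produces many such rises, they fall on all arms alike. They add a common background to each arm and shrink the relative difference that a true excess of fever would show. Because no test is planned, the counts will be judged by eye, so what each count contains matters.

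**Working it through.** The documents state no expected PCS rate for temperature, so there is no figure of the plan to reproduce.

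**Step 1: the logic of the rule (documents only).** With readings to 0.1 °C, the lowest value above 38.5 is 38.6. The rise from baseline B is then 38.6 − B, which is at least 1.1 whenever B ≤ 37.5. For those baselines the absolute part never adds a flag that the change part has not already given. Examples:

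| Baseline → reading | Rise | Above 38.5? | Very High? |
|---|---|---|---|
| 36.0 → 37.1 | 1.1 | no | yes |
| 36.4 → 37.5 | 1.1 | no | yes |
| 36.4 → 38.4 | 2.0 | no | yes |
| 36.5 → 38.6 | 2.1 | yes | yes |
| 37.6 → 38.6 | 1.0 | yes | yes, by the absolute part alone |

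**Step 2: how often normal variation is flagged (assumptions needed).** From the documents: one baseline reading, K = 14 or 17 later readings, 110 subjects per arm. Assumed: normal, independent readings around each subject's own mean; within-subject SD s of 0.2 to 0.4 °C; population mean 36.5 to 36.6 °C; between-subject SD 0.2 to 0.3 °C; no fever, no drug effect, all visits attended. For unrounded readings, the chance of at least one rise of 1.1 or more is

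P = ∫ [1 − Φ(z + 1.1/s)^K] φ(z) dz.

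Simulation with readings rounded to 0.1 °C gives somewhat higher values, because a true difference just under 1.1 can round up to it.

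| s (°C) | Unrounded, K = 14 | Rounded, K = 14 | Rounded, K = 17 | Expected false flags in 110 (rounded, K = 14) |
|---|---|---|---|---|
| 0.20 | 0.06% | 0.14% | 0.16% | 0.15 |
| 0.30 | 4.5% | 6.0% | 6.8% | 6.6 |
| 0.35 | 10.5% | 12.9% | 14.4% | 14.2 |
| 0.40 | 17.9% | 21.0% | 23.1% | 23.1 |

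The last column is 110 times the third. At s = 0.3 to 0.4, roughly 70% to 90% of flagged subjects have a flagged reading of 37.5 or below. Under the same model the share with any reading above 38.5 is below 0.1%.

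**Step 3: what the background does to a comparison by eye.** With background rate b and true fever shares f0 and f1, the tabulated shares are q = 1 − (1 − b)(1 − f), so the difference shrinks to (1 − b)(f1 − f0). Take f0 = 1% and f1 = 10% purely for illustration; the true ratio is 10.

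- b = 0.14%: 1.1% v 10.1%, ratio 8.9
- b = 6%: 6.9% v 15.4%, ratio 2.2
- b = 13%: 13.9% v 21.7%, ratio 1.6
- b = 21%: 21.8% v 28.9%, ratio 1.3

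**Step 4: the table by region.** Japan has 8 subjects per arm, so one flag is 12.5% of an arm. The chance of at least one background flag in such an arm is 1 − (1 − b)^8, which is 1%, 39%, 67% and 85% for the four values of b in Step 3.

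**The case against.** The strongest reply is that nothing is lost. Every reading above 38.5 still meets the rule and appears in the listing with its value. SAP 11.4.1 analyses change in temperature from baseline to each visit and to the minimum, maximum and final values, with contrasts against placebo. Fever reported as an adverse event is tabulated by preferred term under SAP 11.2.2, and Protocol section 8.1.6.1 compares adverse events by Fisher's exact test. Protocol section 5.3.1.1 takes vital signs before any blood draw, and many draws precede the infusion. At those visits the scheduled temperature would miss an acute infusion fever in any case. All of this stands, and it keeps the point small. It does not supply a count of measured fevers by arm. A listing is not a count, a few fevers barely move a mean maximum, and Protocol section 6.1.1.1 makes a vital sign change an adverse event only if it leads to discontinuation, needs treatment or is judged to be one by the investigator.

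A second reply is that a change-only screen is a legitimate choice. Weight is change-only in the same appendix ("Decreased ≥ 7% from baseline"), and a rise from 36.4 to 38.4 is worth flagging. This also stands. It is a reason to keep the change part, but not to pool it with the absolute part.

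A reader might go further and infer that the rule hides a real fever signal. The documents do not support that, for the reasons above and because the dilution is negligible at the low end of the assumed SD. A reader might also infer that the Very Low criterion, "≥ 1.1 decrease from baseline", adds to the problem because it has no absolute limit. It can inflate its own column, but Very Low and Very High are separate columns, so it cannot obscure fever.

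**Conclusion.** The point holds as a minor one about what a descriptive table can show. That the Very High rule reduces to a rise of at least 1.1 for baselines of 37.5 or below follows from Appendix B alone, given readings to 0.1 °C. So does the result that normal readings and fevers share one count.

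The amount of dilution does not follow from the documents. It runs from nothing of note at a within-subject SD of 0.2 to about one subject in five flagged at 0.4. It also assumes independent readings and full attendance; missed visits, or later readings that resemble one another, would lower the rates. The fever shares used for the ratios are illustrative only. No loss of power can be claimed, because SAP 11.4.2 plans no comparison of these counts. Alpha, sample size and the primary analysis are unaffected.

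**What to change.** In SAP Appendix B, replace the single Very High entry for temperature with two separately counted rows: one for readings above 38.5 and one for an increase of at least 1.1 from baseline. Appendix C already sets out QTcF in this way. State in SAP 11.4.2 that each row has its own count per arm and per region.

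The cost is one appendix row and one more line in the PCS table, ideally settled before unblinding. Both existing thresholds stay, every reading flagged now is still flagged, and fever becomes countable by arm. Joining the two parts with 'and' is not advised: it would drop rises such as 36.4 to 38.4, and also 37.6 to 38.6. No change to the Very Low criterion is needed for this purpose.
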